6.1.2. Exclusion Criteria

Potential study patients may not be included in the study if any of the following apply during screening.

[11] Have received treatment within 28 days of the initial dose of study drug with an investigational product or non-approved use of a drug or device (other than the study drug/device used in this study) or are concurrently enrolled in any other type of medical research judged not to be scientifically or medically compatible with this study.

[12] Have serious preexisting medical conditions (left to the discretion of the investigator).

[13] Have symptomatic CNS malignancy or metastasis (screening not required).

Patients with treated CNS metastases are eligible for this study if they are not currently receiving corticosteroids for this indication and/or anticonvulsants, and their disease is asymptomatic and radiographically stable for at least 28 days.

- [14] Have current acute or chronic leukemia.
- [15] Have an active fungal, bacterial, and/or known viral infection including human immunodeficiency virus (HIV) or viral (A, B, or C) hepatitis (screening is not required).
- [16] Have a second primary malignancy that, in the judgment of the investigator and sponsor, may affect the interpretation of results.

Curatively treated nonmelanoma skin cancer or in situ carcinoma of any origin is allowed.
- [17] Have Fridericia-corrected QT interval (QTcF) >480 msec on screening electrocardiogram (ECG).
- [18] Have a serious cardiac condition, such as congestive heart failure; New York Heart Association Class III/IV heart disease; unstable angina pectoris; myocardial infarction within the last 3 months; valvulopathy that is severe, moderate, or deemed clinically significant; or arrhythmias that are symptomatic or require treatment (not including patients with rate-controlled atrial fibrillation).
- [19] Have preexisting corneal diseases that may interfere with assessment of potential toxicity in the eyes during the study.
- [20] Have skin disorders (for example, erythema, and dermatitis) of \geq Grade 2.

6.2. Summary of Study Design

Study JOBA is a multicenter, nonrandomized, open-label, dose-escalation Phase 1 study of IV LY3076226 in patients with advanced or metastatic cancer. Eligible patients will receive LY3076226 as an IV infusion on Day 1 of a 21-day cycle.

Dose escalation for LY3076226 in Part A will be driven by an accelerated dose-escalation scheme. Initial cohorts will enroll at least one patient each until a dose level of 1.6 mg/kg is reached, unless toxicity observed requires enrolling additional patients to a dose level. A modified 3+3 dose-escalation scheme will be followed in subsequent cohorts, with incorporation of a Bayesian model-based dose-escalation method (Neuenschwander et al. 2008) to assist in estimation of the DLT rate at recommended dose levels. Dose levels for Cohorts 2 and beyond will reflect a maximum increment of 100% from the prior dose level. The dose will be escalated until a maximum tolerated dose (MTD) has been identified. If the MTD has not yet been reached at the highest prespecified dose level, then additional dose levels may be investigated based on both safety and the available PK data.

Once MTD is identified in Part A, up to approximately 15 patients who have known alterations of FGFR3 will be enrolled in each of Parts B (urothelial carcinoma) and C (other malignancies) to further evaluate the safety profile of LY3076226, characterize the exploratory biomarker assays, and document any antitumor activity.

Figure JOBA.1 is a representative illustration of the JOBA study design, showing the dose-escalation design in advanced cancer (Part A) and MTD expansions focusing on selected patient populations with known alterations of FGFR3 in urothelial carcinoma (Part B) and other malignancies (Part C).

[figure not shown]

Figure JOBA.1. Illustration of I7O-MC-JOBA study design.

To determine the recommended Phase 2 dose of LY3076226, an adequate sample size is required. A sufficient sample size will allow for an accurate evaluation of the relationship between exposure and toxicity, as well as an evaluation of the relationship between exposure and pharmacological effects using descriptive statistics and appropriate modeling techniques, if data warrant.

The actual sample size of the dose escalation (Part A) will primarily be determined by the observed toxicity and the incidence of DLTs. Under the modified 3+3 dose-escalation scheme, each cohort will include 3 to 6 patients. The anticipated sample size for Part A ranges from approximately 20 to 35 patients, depending on the observed toxicity. Each of Parts B and C expansion cohorts will enroll up to approximately 15 patients. The overall sample size is thus estimated to be approximately 65 patients.

The planned duration of treatment is not fixed. Patients will have tumor assessments after receiving 3 cycles of treatment. Patients without evidence of disease progression may continue treatment until they fulfill one of the criteria for study discontinuation (Section 6.3).

Refer to [Attachment 1](#) for the Study Schedule.

6.2.1. Study Completion and End of Trial

This study will be considered complete (that is, the scientific evaluation will be complete [study completion]) following the protocol-specified final analysis for the primary and secondary objectives.

The end of trial occurs after study completion and after the last patient has discontinued study treatment and completed any applicable continued access follow-up.

6.2.2. Continued Access Period

All patients remaining on study treatment without disease progression following the final analysis for the primary and secondary objectives will be able to enter the continued access period of the study. The continued access period begins after study completion and ends at the end of trial. During the continued access period, patients on study treatment who continue to experience clinical benefit may continue to receive study treatment until disease progression, death, unacceptable toxicity, or start of new anticancer treatment. The continued access period includes a follow-up visit. The follow-up visit begins 1 day after the patient and the investigator agree that the patient will no longer continue treatment in the continued access period and lasts approximately 28 days. If it is deemed to be in the best interest of the patient to start a new anticancer treatment prior to the scheduled end of the follow-up visit, the follow-up visit duration may be shortened. In this case, the follow-up assessments should be completed prior to the initiation of the new therapy.

During the continued access period, all AEs, SAEs, study drug dosing, and dose reduction of treatment will be collected on the case report form (CRF).

Serious adverse events will also be reported to Lilly Global Patient Safety and collected in the pharmacovigilance system (Section 8.1.2.4). In the event that an SAE occurs, additional information (such as local laboratory results, concomitant medications, and hospitalizations) may be requested by Lilly in order to evaluate the reported SAE.

Investigators may perform other standard procedures and tests needed to treat and evaluate patients; however, Lilly will not routinely collect the results of these assessments.

6.3. Discontinuations

If a patient withdraws informed consent, he or she must not be contacted unless he or she has explicitly provided permission and consent. Lilly may continue to use previously collected medical research data prior to the withdrawal consistent with the original authorization.

6.3.1. Discontinuation of Patients

The criteria for enrollment must be followed explicitly. If the investigator site identifies a patient who did not meet enrollment criteria and who was inadvertently enrolled, the sponsor must be notified. If the sponsor identifies a patient who did not meet enrollment criteria and who was inadvertently enrolled, the investigator site will be notified. A discussion must occur between the sponsor clinical research physician (CRP) and the investigator to determine whether the patient may continue in the study, with or without investigational product. Inadvertently enrolled patients may be maintained in the study and on investigational product when the Lilly CRP agrees with the investigator that it is medically appropriate for that patient. The patient may not continue in the study with or without investigational product if the Lilly CRP does not agree with the investigator's determination that it is medically appropriate for the patient to continue. The investigator must obtain documented approval from the Lilly CRP to allow the inadvertently enrolled patient to continue in the study with or without investigational product.

In addition, patients will be discontinued from the study drug and/or from the study in the following circumstances:

- Enrollment in any other clinical trial involving an investigational product or enrollment in any other type of medical research judged not to be scientifically or medically compatible with this study.
- Investigator/Physician Decision
 - The investigator/physician decides that the patient should be discontinued from the study or study drug.
 - If the patient, for any reason, requires treatment with another therapeutic agent that has been demonstrated to be effective for treatment of the study indication, discontinuation from the study drug occurs prior to introduction of the other agent.
- Patient Decision
 - The patient requests to be discontinued from the study or study drug.
- Sponsor Decision
 - Lilly stops the study or stops the patient's participation in the study for medical, safety, regulatory, or other reasons consistent with applicable laws, regulations, and GCP.
- The patient has radiographic progressive disease or significant symptomatic disease deterioration characterized as progression of disease, in the opinion of investigator, in the absence of radiographic evidence of progressive disease.
- The patient experiences unacceptable toxicity.
- The patient is noncompliant with study procedures and/or treatment (Section 7.6).
- The patient's dosing is delayed for more than 2 weeks as the result of an AE that is at least possibly related to LY3076226. If this delay occurs for the start of Cycle 2, this will be considered a DLT.

6.3.2. Discontinuation of Study Sites

Study site participation may be discontinued if Lilly, the investigator, or the ethical review board (ERB) of the study site judges it necessary for any scientific, medical, safety, regulatory, ethical, or other reasons consistent with applicable laws, regulations, and GCP.

6.3.3. Discontinuation of the Study

The study will be discontinued if Lilly, while considering the rights, safety, and well-being of the patient(s), judges it necessary for any scientific, medical, safety, regulatory, ethical, or other reasons consistent with applicable laws, regulations, and GCP.

7. Treatment

7.1. Materials and Supplies

LY3076226 drug product is supplied for clinical trial use as an aqueous solution (10mM acetate, 9% sucrose, 0.01% polysorbate 20, pH 5.0) at a concentration of 5.0 mg/mL (in terms of antibody weight). It is a clear to slightly opalescent, colorless to slightly brown or slightly yellow liquid. The drug product is supplied as a single-use vial containing 100 mg LY3076226 in 20 mL of solution (5.0 mg/mL). LY3076226 will be administered as an IV infusion and sterile dextrose (5%) solution only must be used as a diluent. Lilly instructions regarding dilution requirements should be followed.

Clinical study materials will be labeled according to the country's regulatory requirements.

7.2. Study Drug Administration

The investigator or designee is responsible for:

- explaining the correct use of the investigational agent to the site personnel,
- verifying that instructions are followed properly,
- maintaining accurate records of study drug dispensation and collection, and
- returning or destroying all unused medication to Lilly or its designee at the end of the study.

Patients will be instructed to contact the investigator as soon as possible if they have a complaint or problem with the study drug so that the situation can be assessed.

7.2.1. Dosing Schedule

For doses \leq 250 mg, LY3076226 will be administered as an IV infusion over approximately 60 minutes on Day 1 of each 21-day cycle. The sponsor may instruct the sites to extend the infusion time for up to 2 hours for doses greater than 250 mg. The assigned dose and duration of infusion of LY3076226 will be provided by the sponsor on a patient registration form. Subsequent doses should be adjusted as described in Section [7.2.6](#).

Premedication is not permitted for the initial dose of LY3076226 for each patient so that any observed toxicities may be appropriately characterized.

7.2.2. Dose Escalation

7.2.2.1. Dose-Limiting Toxicity Determination and Maximum Tolerated Dose Definition

Dose-limiting toxicity (DLT) is defined as an AE occurring during Cycle 1 that is at least possibly related to LY3076226 and fulfills any one of the following criteria using the NCI-CTCAE v 4.0:

- CTCAE Grade ≥ 3 non-hematological toxicity. Exceptions will be made for the following:
 - Nausea, vomiting, diarrhea, and constipation that can be controlled with treatment (Grade 3 and Grade 4 nausea, vomiting, or diarrhea should be considered DLTs if persisting for more than 48 hours, despite supportive intervention.)
 - Anorexia
 - Grade 3 fatigue lasting ≤ 5 days
- Grade 3 elevations of ALT and/or AST lasting >7 days.
- Concurrent elevation of ALT $>3 \times$ ULN and total bilirubin $>2 \times$ ULN in the absence of biliary obstruction or other causes that could reasonably explain the elevation.
- CTCAE Grade 4 neutropenia of >7 days' duration
- Any febrile neutropenia
- CTCAE Grade 3 thrombocytopenia with bleeding
- CTCAE Grade 4 thrombocytopenia with or without bleeding
- Any other significant toxicity deemed by the primary investigator and Lilly clinical research personnel to be dose limiting (for example, any toxicity that is at least possibly related to the study medication and that requires the withdrawal of the patient from the study during Cycle 1 or delays the start of Cycle 2 by >14 days).

For the purpose of this study, the MTD is defined as the highest dose tested that has less than 33% probability of causing a DLT.

7.2.2.2. DLT-Equivalent Toxicity

A DLT-equivalent toxicity is defined as an AE occurring during Cycle 2 and beyond that would have met the criteria for a DLT if it had occurred during Cycle 1. For individual patients experiencing a DLT-equivalent toxicity, dose adjustments will be made as outlined in Section 7.2.6. At each interim analysis (as defined in Section 10.10), the rate of DLT-equivalent toxicities will be assessed. If the rate of DLT-equivalent toxicities is unacceptable (for example, a DLT-equivalent toxicity is observed in $>33\%$ patients at a given dose level), the data will be reviewed by study investigators and the Lilly CRP/clinical research scientist (CRS) and a safety analysis may be triggered. If the findings indicate that a dose level does not have an acceptable safety profile for chronic (Cycle 2 or later) administration, then a lower dose level will be chosen for further investigation. This decision will be documented in writing.

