In the 5-week monkey study, haze at the corneal limbus was seen by slit-lamp examination after 5 treatments in all animals treated at 3 mg/kg and was accompanied by corneal pigmentation in the majority of the affected animals. Microscopically, increased mitoses and single-cell necrosis were present in the corneal epithelium at all dosages; dyskeratosis was seen in animals treated at 3 mg/kg or more. After the 8-week recovery period, the corneal hazing was not present, although pigmented corneas were still apparent – dyskeratosis and/or pigment were seen histologically. Corneal pigmentation observed in recovery animals is a likely sequelae of the corneal injury noted in terminal and early death animals. In the rat, although no corneal lesions were seen by ophthalmic examination, increased mitoses in the corneal epithelium were seen at all dosages after 5 weeks of treatment; this change was not apparent after the 8-week reversibility period.

Single-cell necrosis and increased mitoses were seen in the epithelium of some or all of the GI tract in both rats and monkeys at the highest dose; these changes were completely reversible after 8 weeks of recovery.

Effects on the bone marrow and lymphoid tissues, with concomitant effects on circulating red and white blood cells, were consistent with the cytotoxic activity of the DM4 payload. These changes were most severe at the high dose in rats and monkeys and comprised decreased erythroid and early myeloid progenitors and increased mitoses/single-cell necrosis in the bone marrow, increased mitoses and/or decreased cellularity of lymphoid tissue, decreased erythroid mass and decreased reticulocyte, neutrophil, lymphocyte, monocyte, and eosinophil counts; at the lower dosages, these effects were less severe and/or frequent in both species. Effects on bone marrow, blood, and lymphoid tissue showed complete or almost complete recovery during the 8-week reversibility period.

In male rats, tubular degeneration in the testis and hypospermia/inflammation in the epididymides were seen at the highest dose (10 mg/kg) and in 1 or 2 males at the 3-mg/kg dose; no similar changes were seen at 1 mg/kg. The effects on testes and epididymides were only partially reversible.

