If, during dose escalation, a situation presents itself that is not described above, Lilly CRP/CRS and investigators will determine the best method to select the appropriate dose for the patient(s) involved, using all available information. The decision will be documented in writing. No dose escalation can occur without prior discussion and agreement between the site-specific investigator and the Lilly CRP/CRS. Written notification will be sent to the site specifying the dose to be used for each patient at each dose level.

Table JOBA.3. Example of LY3076226 Dose Levels for Part A

Cohort	LY3076226 Dose Level (mg/kg)
1	0.2
2	0.4
3	0.8
4	1.6
5	2.4
6	3.2
7	4.0
8	5.0

Based on the ongoing safety reviews, modifications to the dose-escalation strategy or other design elements may be made via protocol amendment to ensure patient safety.

7.2.3. Dose Confirmation in Patients with Known Alterations of FGFR3 (Parts B and C)

Once the MTD has been defined in Part A, Parts B (urothelial carcinoma) and C (other malignancies) will be activated and will enroll up to approximately 15 patients who have known alterations of FGFR3, to further define the safety and tolerability of LY3076226 and to characterize the exploratory biomarker assays. The dose of LY3076226 in Parts B and C will not exceed the MTD of LY3076226, as defined during dose escalation in Part A. The exact sample size of this cohort will be dependent on the number of patients who have known FGFR3 alterations treated at the MTD during dose escalation in Part A, and will be adjusted so that a total of approximately 15 patients will be treated.

If a DLT-equivalent toxicity occurs in one third or more of patients during Cycle 1 (with a minimum of 6 patients enrolled), the enrollment of new patients will cease until the Lilly CRP/CRS and investigators assess the severity and nature of the toxicities. A data review will be performed to determine whether to continue at the current LY3076226 dose or whether the dose of LY3076226 should be reduced. The toxicity-band method used in the dose-escalation phase will be updated with the additional data observed in Parts B and C to confirm the MTD selection and/or to inform any need to further refine the MTD. This decision will be documented in writing.

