10.10. Interim Analyses

Once the LY3076226 MTD is defined for Part A, an interim analysis will be performed prior to opening Parts B and C.

At the end of Parts B and C, an analysis may be conducted to review available safety, PK, and efficacy data once all evaluable patients have either completed 3 cycles of study treatment or discontinued from the study treatment.

Because this is a dose-finding study, data will be reviewed on a cohort-by-cohort basis during the study, until the MTD is determined for Part A. The purpose of these cohort-by-cohort reviews is to evaluate the safety data and any available PK data at each dose level and determine if a DLT has been observed that would suggest MTD has been met or exceeded. The investigators and the Lilly study team will make the determination regarding dose escalation based upon their review of the safety and tolerability data as described in this protocol.

In Parts B and C, if a DLT-equivalent toxicity occurs in one third or more of patients during Cycle 1 (with a minimum of 6 patients enrolled), a data review will be performed to determine whether to continue at the current LY3076226 dose or whether the dose of LY3076226 should be reduced. Refer to Section [7.2.3](#) for more details.

If an unplanned interim analysis is deemed necessary, the sponsor will determine if it is necessary to amend the protocol.

11. Informed Consent, Ethical Review, and Regulatory Considerations

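### While Parts B and C are being treated, no pre-specified, rate-based review of Cycle 2-and-later toxicity operates; the only planned look that remains is optional and comes at the end

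*Protocol*

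**What the plan says.** Protocol Section 7.2.2.2 sets the definition: "A DLT-equivalent toxicity is defined as an AE occurring during Cycle 2 and beyond" that would have been a DLT in Cycle 1. It then sets the timing: "At each interim analysis (as defined in Section 10.10), the rate of DLT-equivalent toxicities will be assessed". If the rate is unacceptable (the example given is more than 33% of patients at a dose level), investigators and the sponsor's clinical research staff review the data. If the dose proves unacceptable for chronic administration, a lower level is chosen for further investigation.

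Section 10.10, repeated in SAP Section 6.15, lists the looks:

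- Once the Part A MTD is defined, "an interim analysis will be performed prior to opening Parts B and C". This look is mandatory.
- A later look is permissive: "At the end of Parts B and C, an analysis may be conducted to review available safety, PK, and efficacy data". It waits for every evaluable patient to finish 3 cycles or come off treatment.
- In Part A, "data will be reviewed on a cohort-by-cohort basis during the study, until the MTD is determined for Part A".
- In Parts B and C, a data review is triggered by DLT-equivalent toxicity in one third or more of patients during Cycle 1, with at least 6 enrolled.
- An unplanned interim analysis is possible, with no criterion given.

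Section 7.2.3 states the fourth item with its consequence: "If a DLT-equivalent toxicity occurs in one third or more of patients during Cycle 1 (with a minimum of 6 patients enrolled"), new enrollment ceases until the toxicities have been assessed.

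**The concern.** Section 7.2.2.2 is the protocol's own aggregate test of whether a dose can be given repeatedly. It is tied to interim analyses, and the mandatory one falls before the expansions open. Parts B and C are where most repeated dosing at the selected dose would occur, and one of their stated purposes is to define safety and tolerability further. The check therefore lapses at the stage that should inform it most.

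Later-cycle events are plausible for this drug. Section 5.3.3 names skin and corneal changes among the expected DLTs and reports that "haze at the corneal limbus was seen by slit-lamp examination after 5 treatments in all animals treated at 3 mg/kg" in the 5-week monkey study. In Attachment 1, the only scheduled on-treatment ophthalmic examination falls in Cycle 3, between Days 15 and 21. A corneal finding from that visit arises after Cycle 1, so the expansion trigger as worded would not count it.

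At stake is whether a raised later-cycle rate at the selected dose would prompt a defined group review while the expansions could still be adjusted, or only once they are over.

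**Working it through.** **Expansion size.** Protocol Section 6.2 gives about 20 to 35 patients in Part A and up to about 15 in each of Parts B and C. The upper end gives 35 + 15 + 15 = 65, the stated overall total, so the expansions hold about 15 + 15 = 30. Section 7.2.3 can also be read as about 15 in all; the argument is the same with 15.

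**Which looks cover Cycle 2 and later during Parts B and C?**

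| Look | Operates during expansion? | Pre-specified later-cycle check? |
|---|---|---|
| Interim analysis after the Part A MTD | No, it precedes opening | Yes, through 7.2.2.2 |
| Cohort-by-cohort reviews | No, they end at the MTD | Not stated |
| One-third rule (7.2.3, 10.10, SAP 6.15) | Yes | No, Cycle 1 only |
| End-of-expansion analysis | No, and optional | Through 7.2.2.2, if held |
| Unplanned interim analysis | Possibly | No criterion |

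No row has both. The last expansion patient must have completed 3 × 21 = 63 days or stopped treatment before the end-of-expansion analysis.

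**The one-third rule against the definition.** Taken with the definition in Section 7.2.2.2, a DLT-equivalent toxicity cannot occur during Cycle 1, so the rule counts nothing. Read as Cycle 1 DLTs, it works but does not reach later cycles. The toxicity-band update in Section 7.2.3 models the probability of a DLT, which Section 7.2.2.1 confines to Cycle 1.

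**How much the pre-expansion interim analysis can show.** Assume 6 patients at the MTD, all reaching Cycle 2, and a true later-cycle rate of 40%. The documents give none of these.

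- P(2 or more of 6) = 1 − 0.6⁶ − 6(0.4)(0.6⁵) = 1 − 0.0467 − 0.1866 = 0.77.
- P(3 or more of 6) = 0.767 − 15(0.4²)(0.6⁴) = 0.767 − 0.311 = 0.46.

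Which figure applies depends on the threshold. Two of 6 is 33.3%: it meets one third or more, and literally exceeds 33%, but it is not more than one third.

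**Illustration of extending the review.** Count patients one at a time, from n = 6 to n = 15. With x patients having had an event, a review is called the first time 3x ≥ n (one third or more) or 3x > n (more than one third). Patients are independent, all reach Cycle 2, and outcomes are known at once. Exact binomial recursion gives the chance of at least one review:

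| True later-cycle rate | One third or more | More than one third |
|---|---|---|
| 10% | 0.13 | 0.04 |
| 20% | 0.42 | 0.25 |
| 40% | 0.90 | 0.81 |
| 50% | 0.97 | 0.94 |
| 60% | 0.996 | 0.99 |

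**The case against.** The strongest reply is that later-cycle toxicity is not unwatched. A reader might infer that Section 7.2.2.2 is the only rule acting after Cycle 1. It is not:

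- Section 7.2.6.1 and Table JOBA.4 govern dosing in every cycle.
- Section 6.3.1 discontinues patients for related delays of more than 2 weeks.
- Section 8.1.4 sets a hepatic threshold with an action.
- Section 8.1.2 has investigator, monitor and sponsor reviewing data regularly.
- Section 7.2.2.3 allows amendment after ongoing safety reviews, and Section 10.10 allows unplanned analyses.
- Section 4 defines an interim analysis broadly, so a review held during expansion might count as one.

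In an open-label Phase 1 study of this size, reliance on judgement is partly a design choice. All of this stands. But the first three act on individual patients, and the others set no aggregate rate and no time for a later-cycle review. The sponsor evidently wanted such a check, because it wrote one.

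A reader might also infer that the RP2D could be chosen with no safety review. Section 7.2.4 rules that out: the RP2D follows Parts B and C and includes an assessment of safety, PK and PD data. What remains is a mismatch between that requirement and the optional analysis in Section 10.10.

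The nonclinical support needs qualifying too. Section 5.3.3 says the animal schedule was more intense than the clinical one, and that the changes are considered manageable and at least partly reversible.

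**Conclusion.** The point holds as a gap in pre-specified aggregate review, not as an absence of safety oversight. As written, the number of pre-specified, rate-based reviews of Cycle 2-and-later toxicity during Parts B and C is zero, for about 30 patients. That follows from the text and rests on no assumed rate. It does not mean that the chance of any review is zero, since discretionary review stays open.

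The probabilities in the working show only how often an existing threshold would call a review. They rest on assumed true rates, independence and immediate outcomes, and they do not support a claim about how many patients would be spared exposure. Table 3 of Attachment 10 should not be enlisted either: it simulates Cycle 1 DLTs and says nothing about later cycles.

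The sponsor should act on this. The protocol's own check on chronic dosing stops operating just as repeated dosing at the selected dose expands, and restoring it is cheap.

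**What to change.** Reconcile Protocol Sections 7.2.2.2, 7.2.3 and 10.10 and SAP Section 6.15 so that the existing Section 7.2.2.2 review, with its present reviewers and actions, also applies during Parts B and C. The text should state:

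- which cycles each trigger covers, removing the conflict between the definition and the Cycle 1 wording;
- when the Cycle 2-and-later rate is assessed during expansion;
- which existing threshold applies (more than 33%, or one third or more), and whether exactly one third meets it;
- whether reaching it pauses enrollment, as in Section 7.2.3, or prompts a data review only.

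These values are for the sponsor to set. The permissive wording for the end-of-Parts-B/C safety analysis in Section 10.10 and SAP Section 6.15 should be made firm, to match the safety assessment that Section 7.2.4 already requires.

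The cost is protocol and SAP wording, with no new visits or data. The downside is some extra reviews at tolerable doses. In the 15-patient illustration with a minimum of 6, the chance of at least one is about 42% at a true rate of 20% under one third or more, and about 25% if more than one third is required.
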